15.4 Primary Efficacy Endpoint: Post-treatment Control

All subjects will undergo a treatment interruption designed to evaluate the primary outcome of “post-treatment control” (PTC), using the definition we recently used as part of the CHAMP Cohort collaboration¹³². In this study, PTCs were defined as individuals who remained off ART for ≥ 24 weeks and maintained viral loads ≤ 400 copies/mL for at least 2/3 of the time points. Viral loads > 400 HIV-1 RNA copies/mL were acceptable if the participant was subsequently able to suppress the viral load back to ≤ 400 HIV-1 RNA copies/mL and maintained virologic control for 24 weeks.

In our protocol, a combination of two bNAbs will be administered at the time ART is interrupted, and will likely have a persistent antiviral effect until levels wane to subtherapeutic levels, which we will assume to occur at about Week 12 of the ATI period. Also, we expect that in the post-ART and post-bNAb phase of the ATI that a period of acute viremia will occur, and that this could last for up several weeks. As described in Section 1.11, ART will be initiated if plasma HIV RNA levels remain consistently $> 50,000$ copies RNA/mL for four weeks, $> 10,000$ copies RNA/mL for six weeks, > 2000 copies RNA/mL for $>$

12 weeks, and > 400 copies RNA/mL > 24 weeks. In this scenario, post-treatment control will only be achieved once viremia falls below 400 copies RNA/mL and remains there for 24 weeks.

Success will hence be defined in two ways. First, subjects who fail to show any consistent rebound above 400 copies RNA/mL between Week 12 of the ATI (when bNAbs levels wane) and Week 36 of the ATI will be considered as having achieved post-treatment control. Second, subjects who exhibit a rebound and eventually achieve 24 weeks of virus control will be considered as having achieved post-treatment control.

Failure will be defined based on the need to resume ART due to high-level viremia, dropping CD4+ T cell counts, or clinical events (see Section 1.11).

The proportion of individuals who achieve our study-defined PTC will be the primary outcome.

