1.3 Product Dosing

| Product Name | Dose | Administration route | Frequency | Comment |
|--------------------------------------|----------------------|--|-------------------|--|
| p24CE1/2 plasmid DNA | 2-4 mg (see comment) | IM injection by electroporation (TriGrid Delivery System v1.0) | Weeks 0, 4 and 12 | 
Week 0:
 
 • 2mg in injection site #1 • 2mg in injection site #2 
Week 4:
 
 • 2mg in injection site #1 • 2mg in injection site #2 • 
Week 12:
 
 • 2mg in injection site #1 
2mg in injection site #2
 |
| p55^{gag} plasmid DNA | 2mg (see comment) | IM injection by electroporation (TriGrid Delivery System v1.0) | Week 12 | 
Week 12:
 
 • 1mg in injection site #1 
1mg in in injection site #2
 |
| IL-12 plasmid DNA | 2mg (see comment) | IM injection by electroporation (TriGrid Delivery System v1.0) | Weeks 0, 4 and 12 | 
Week 0:
 
 • 1mg in injection site #1 • 1mg in in injection site #2 
Week 4:
 
 • 1mg in injection site #1 • 1mg in in injection site #2 
Week 12:
 
 • 1mg in injection site #1 |

| | | | | |
|------------------------------|------------------------|-------------------------|------------------------------|---|
| | | | | 1mg in in injection site #2 |
| MVA/HIV62B (MVA62B) | 10 ⁸ TCID50 | IM injection (deltoid) | Week 20 | MVA boosting typically scheduled for 8 weeks after last DNA prime |
| 10-1074 | 30 mg/kg | Intravenous infusion | Weeks 24 and 34 | Half-life of 20-23 days; therapeutic levels (> 10 ug/mL) expected for at least 8 weeks; pre-ATI infusion to occur two days before ART is interrupted; 10-1074 will be administered first, the line will be flushed, and then VRC07-532LS will be administered |
| VRC07-523LS (VRC07) | 20 mg/kg | Intravenous infusion | Weeks 24 and 34 | Formal PK analysis pending; therapeutic levels (> 10 ug/mL) expected for at least 12 to 16 weeks; pre-ATI infusion to occur two days before ART is interrupted; 10-1074 will be administered first, the line will be flushed, and then VRC07-532LS will be administered |

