9.10 Pharmacokinetic Measurements

Broadly neutralizing antibody (10-1074, VRC07-523LS) levels will be measured at indicated visits during Stages 4 and 5. Plasma samples will be collected every 2 weeks for 10 weeks during Stage 4 (bNAbs/lefitolimod) and every two weeks for 24 weeks during the Stage 5 (bNAbs/ATI).

[figure not shown]
[figure not shown]
VRC07 levels will be measured at the Vaccine Immunology Testing Laboratory (VITL) located at the VRC using well-validated assays. Concentrations of VRC07-523LS for the PK analyses will each be measured by qualified ELISAs using a Beckman Biomek based automation platform. Briefly, the VRC07-523LS anti-idiotypic MAb is coated onto Immulon-4HXB microtiter plates overnight at 4° C. Plates are washed and blocked (10% FBS in PBS) for 2 hours at room temperature. Duplicate serial 3-fold dilutions covering the specific range (100 – 218,700) of the test sample are incubated for 2 hours at 37°C followed by horseradish peroxidase - labeled goat anti-human antibody (1 hour, 37° C), and TMB substrate (15 minutes, room temperature). Color development is stopped by addition of sulfuric acid and plates are read within 30 minutes at 450 nm via the Molecular Devices Paradigm plate reader. Linear regression of a standard curve of VRC07-523LS covering the linear range is utilized to quantitate the sample concentrations of each antibody based upon the average of sample dilutions within the range of the assay.

Similarly, 10-1074 levels will be measured at using a validated ELISA; it is expected that these assays will be performed by [name] and her colleagues using a BMGF-funded core laboratory.

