9.12 Cellular Immunologic Measurements

T cell immunogenicity. High-resolution multi-parameter flow cytometric intracellular cytokine staining (ICS) assays will be used to longitudinally monitor the induction, differentiation, and durability of HIV-specific T cell responses in the peripheral blood. PBMCs will be stimulated *in vitro* with peptides from each of the seven CE regions, or peptide pools of overlapping 15mers derived from Gag, Pol, Env, or Nef (using potential T cell epitope peptides, PTE; NIH AIDS Reagent Program). ICS will be performed on two baseline PBMC samples, and these will be compared to newly-generated T cell responses detectable in PBMCs after the electroporations (Week 20), at the peak of the vaccine response (Week 22 of the study, 2 weeks after the MVA boost), pre-ATI (Week 34 of the study, after a dose of bNAbs and 9 weekly lefitolimod injections), at Week 38 and 42 (approximately when bNAb levels are anticipated to become undetectable), and at Week 54.

The focus of our immunogenicity studies will be to measure: (1) the number of new CE-targeted CD4+ and CD8+ T cell responses elicited by therapeutic vaccination, as well as (2) the magnitude, (3) polyfunctionality (number of effector cytokines including IFN- γ , TNF- α , and IL-2 are by responding cells), and (4) cytotoxic phenotype (expression of Perforin, Granzyme B and degranulation as measured by CD107a upregulation) of the CE-targeted responses. Because the vaccine regimen may also stimulate non-CE Gag responses (with the vaccine dose that includes p55 Gag), as well as Pol and/or Env responses (with the MVA62B vaccine), we will assess these broader responses in parallel (with Nef as a negative control).

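### The no-rebound route to post-treatment control starts at a fixed ATI week 12, although the plan's own expectation for VRC07-523LS runs to week 16 or beyond and the measured antibody levels are not used

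*Combined protocol and SAP*

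**What the plan says.** Section 15.4 gives two routes to post-treatment control (PTC).

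- **No-rebound route.** There must be no consistent rebound above 400 copies/mL "between Week 12 of the ATI (when bNAbs levels wane) and Week 36 of the ATI". The starting point is the time the antibodies are taken to have become subtherapeutic, "which we will assume to occur at about Week 12 of the ATI period".
- **Rebound route.** Here "subjects who exhibit a rebound and eventually achieve 24 weeks of virus control will be considered as having achieved post-treatment control". Neither a starting week nor an antibody level is attached.

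The plan dates the loss of antibody in several places (study week 34 is ATI week 0):

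| Place | Statement | ATI week |
|---|---|---|
| Section 1.3, VRC07-523LS | "Formal PK analysis pending; therapeutic levels (> 10 ug/mL) expected for at least 12 to 16 weeks" | 12 to 16 or later |
| Section 1.3, 10-1074 | "Half-life of 20-23 days; therapeutic levels (> 10 ug/mL) expected for at least 8 weeks" | 8 or later |
| Synopsis, Study Design, Stage 5 | therapeutic to study week 42 or later | 8 or later |
| Section 9.12 | "at Week 38 and 42 (approximately when bNAb levels are anticipated to become undetectable" | 4 to 8 |
| Section 15.4 | subtherapeutic, by assumption | about 12 |

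Section 9.10 has both antibodies measured "every two weeks for 24 weeks during the Stage 5 (bNAbs/ATI", and the schedule in section 10.12 agrees (study weeks 34 to 58). No endpoint rule refers to these levels.

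Section 15.6 tests the early-ART group (N=15) against 15%, the most PTC that the literature review would lead one to expect without intervention. The synopsis states a different primary endpoint: for people who do not rebound, control through week 24 of the interruption.

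**The concern.** By starting at week 12 rather than week 0, section 15.4 accepts that time under active antibody should not count as control. It then applies that principle with one assumed date for everyone. That date is the earliest end of the range the plan gives for the longer-lasting antibody, and formal pharmacokinetic analysis was still pending. A second dose ten weeks after the first (study weeks 24 and 34) adds residual drug.

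If VRC07-523LS is still active after week 12, part of the 24 control weeks is passive suppression. The rebound route is open to the same problem, because control regained while antibody is present could count. There is no concurrent control arm, and the null describes people who received no antibody. Antibody lasting past week 12 can therefore only push the count of successes upwards. The primary efficacy conclusion could then partly reflect drug still in the blood.

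**Working it through.** **1. The plan's own rule.** With X binomial (15, 0.15), P(X ≥ 6) = 0.0168, and the two-sided likelihood ratio P-value for 6/15 is 0.019. For 5/15 the values are 0.062 and 0.077, so 6 is the right threshold. Power at a true rate of 47% is 78.8%, within about a point of the stated 80%; it is 79.9% at 47.5% and 81.0% at 48%. The design reproduces.

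**2. Overlap on the documents' figures.** If antibody is therapeutic to ATI week W, the covered part of the window is W − 12 weeks.

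- W = 12: 0 of 24 weeks.
- W = 16: 4 of 24 weeks (17%), leaving 20 antibody-free.

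Section 1.3 sets no upper limit, so more is possible.

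**3. Effect of the earlier dose (assumption needed).** The VRC07-523LS half-life cannot be read in the public copy. Assume single-exponential decay with half-life h of 4 to 6 weeks, and let one dose cross 10 ug/mL at T weeks. Two equal doses ten weeks apart then cross at T + h·log2(1 + 2^(−10/h)).

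| T | h = 4 | h = 6 |
|---|---|---|
| 12 | 12.9 | 14.4 |
| 16 | 16.9 | 18.4 |

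**4. What overlap does to the false-positive rate.** Let f = 36 − W be the antibody-free weeks in the window. Scale each no-effect model so that 15% are rebound-free after 24 antibody-free weeks. The rebound models are assumptions.

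- *Constant hazard:* λ = −ln(0.15)/24 = 0.0790 per week, and S(f) = exp(−λf).
- *Mixture:* S(f) = c + (1 − c)·2^(−f/m), where m is the median rebound time in those who rebound and c is set so that S(24) = 0.15.

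For W = 16, f = 20:

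| No-effect rebound model | Background rate | P(X ≥ 6 of 15) |
|---|---|---|
| All rebounds within 20 antibody-free weeks | 15.0% | 1.7% |
| Mixture, m = 2 weeks | 15.1% | 1.7% |
| Mixture, m = 4 weeks | 16.3% | 2.5% |
| Mixture, m = 6 weeks | 18.3% | 4.2% |
| Constant hazard | 20.6% | 6.9% |

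At W = 12 every model gives 1.7%. The background must exceed about 19% before P(X ≥ 6) passes 5%.

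**5. Room for a level-based start.** Follow-up to study week 86 is ATI week 52, so a 24-week window fits for any start up to ATI week 52 − 24 = 28. With two-weekly samples, the crossings in step 3 are first seen at weeks 14, 16, 18 and 20, and windows end at ATI weeks 38 to 44.

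**6. Synopsis rule.** Control through ATI week 24, with washout at week 12 to 16, leaves 24 − 16 = 8 to 24 − 12 = 12 antibody-free weeks.

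**The case against.** The strongest reply is that the no-rebound route still requires control to week 36. The synopsis expects rebound a few weeks after levels become subtherapeutic, so a passively suppressed participant would normally rebound inside the window and fail that route. This stands, and it is why the lower end of the range is no material inflation.

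Four more points count for the plan. The 15% is stated as a maximum, so the true background may be lower. Week 12 is later than the waning times in section 9.12; if those are right, the fixed clock is if anything strict. The fixed start governs only one route, and the synopsis expects everyone to rebound even if the approach works, so the other route may supply most successes. Coverage beyond week 16 rests on an assumed half-life.

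Stronger readings are tempting. A reader might infer a background rate of 25% or 30% and a correspondingly large false-positive rate. Nothing in the documents links a 0-to-4-week overlap to such rates. They would need washout well past week 16 together with slow rebound, which runs against the synopsis. A reader might also infer that passive and immune control cannot be told apart afterwards. The two-weekly levels and the weekly, later two-weekly, viral loads allow that comparison for each participant. What is missing is a pre-specified rule for using them.

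**Conclusion.** The point holds in limited form. The plan has no single waning assumption, and the one used for the endpoint is the earliest end of its own range for VRC07-523LS. The rebound route has no antibody condition, and measured levels that would settle the question are left out of the endpoint. On the documents' figures the overlap is 0 to 4 of 24 weeks. With washout at ATI week 16 the false-positive rate lies between about 1.7% and about 7%, against 1.7% as designed. The upper figure needs a constant rebound hazard, and the calculation takes 15% as the true antibody-free rate. The bias may be nil, but antibody lasting past week 12 can only act towards success. The documents do not show that the primary test is badly inflated. They do show that it depends on an unverified date where a measured one is available. The change is worth making because it applies the plan's own principle at little cost.

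**What to change.** In section 15.4:

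1. Start each participant's 24-week control window at the later of ATI week 12 and the first scheduled sample with both antibodies below a pre-specified level, for example the 10 ug/mL used in section 1.3.
2. Apply the same antibody condition to the 24 weeks of control in the rebound route.
3. Keep the fixed week-12 clock as a sensitivity analysis, and add one using the assay's lower limit.
4. State the rule for missing levels, since sections 10.8 and 10.12 and Appendix C allow storage to be deferred at remote visits.
5. State the rule for levels still above threshold at ATI week 24, for example by testing plasma stored at Weeks 62, 70 and 78. Only Week 62 (ATI week 28) still leaves a full 24 weeks before Week 86, so later crossings need an explicit classification.

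Reconcile the waning statements in the synopsis (Stage 5) and sections 1.3, 9.12 and 15.4. Separately, reconcile the synopsis week-24 endpoint with section 15.4.

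The cost is SAP wording and possibly a few extra assays on stored plasma. No dose, visit or ART-restart rule changes. Some windows end later, at about ATI week 38 to 44 under the half-lives assumed above, still before Week 86 (ATI week 52).

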| | 
of individuals who achieve PTC will be tabulated and a 2-sided 95% confidence interval obtained by exact calculations for the binomial distribution. The proportion will also be compared to historical controls, with a P-value obtained by likelihood ratio test. For those who initiated ART during acute infection, a literature review indicates that no more than 15% PTC would be expected without intervention. For those who initiated during chronic infection, no more than 5% PTC would be expected. These maximum expected rates will serve as the null hypothesis for our P-value calculations. Evaluation of the acute group will be the primary analysis, while evaluation of the chronic group will be exploratory and provide initial preliminary information on generalizability.
 
Using standard and innovative measures of immunogenicity, we will determine the capacity of our strategies to stimulate broad, functional T cell responses against conserved element HIV epitopes, and comprehensively characterize the impact of the vaccine on several innate and adaptive immune parameters. The size of the active and latent reservoirs before, during and after vaccination will be measured.
 |
| SAMPLE SIZE JUSTIFICATION | 
For the acute group, observing 6 or more PTC among N=15 (40%) will result in $P < 0.05$ versus the null hypothesis of 15%, and the study will have $\geq 80\%$ power if the true chance of PTC with intervention is $\geq 47\%$.
 
For the chronic group, observing even one PTC (20%) would provide some indication of promise, and observing 2 PTC (40%) would produce $P < 0.05$ versus the null hypothesis of 5%.
 |
| PLANNED INTERIM ANALYSES | 
A Safety Monitoring Committee (SMC) will be convened and will meet biannually to review all adverse events and the conduct of the study. Serious adverse events will be monitored by the committee on an ongoing basis throughout the study.
 |

TABLE OF CONTENTS

| | | |
|----------|--|-----------|
| 1 | BACKGROUND | 23 |
| 1.1 | Study background and rationale..... | 23 |
| 1.1.1 | CD8+ T cell immunity in a therapeutic setting | 23 |
| 1.1.2 | Prime-boost vaccine regimen followed by a TLR7 agonists..... | 24 |
| 1.1.3 | TLR7 agonists during ART can induce an SIV cure/remission..... | 24 |
| 1.1.4 | Emerging role of ADCC responses in a therapeutic setting | 25 |
| 1.1.5 | TLR7 agonists and bNAbs induce an SIV cure/remission | 25 |

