7 CONCURRENT MEDICATIONS

All subjects should be maintained on the same medications throughout the entire study period, as medically feasible.

Subjects must provide their own antiretroviral drugs. No restrictions will be placed on the antiretroviral drug combinations. If medically feasible, study participants will be encouraged to remain on their entry antiretroviral regimen through week 34 of the study.

Participation in the study will not interfere in any manner with the subject's standard of care.

Given the potential immune-modifying activities of the vaccine and IL-12 adjuvants, other immunomodulatory drugs (e.g., cytokines, systemic corticosteroids, most biologics) will be discouraged if medically feasible.

Routine or standard of care vaccinations (such as influenza, pneumococcal, and meningococcal vaccinations) are allowed and documented in the case report forms.

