9.1 Concomitant Medications

All concomitant medications taken within 30 days prior to screening and entry and a complete history of ART, HIV-1 related vaccines, and immune-based therapies will be documented at the Screening and Entry visits.

At each subsequent visit, all additions or discontinuations of prescription medications should be recorded. Actual or estimated start and stop dates should be recorded.

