The schedule during the ATI period will be defined by clinical course and the characteristics of any virus rebound. ART will be initiated for clinical events, sustained drop in CD4+T cell counts or sustained increased in viremia. Prior to these events, subjects will be followed weekly for 24 weeks and then every two weeks. Once ART is initiated, subjects will be followed at the time of ART restart, and at 4, 8, and 24 weeks after restart.

Note: In cases in which clinical laboratory testing is performed remotely (for example, if trying to minimize in-person visits during the ATI for individuals living outside of San Francisco during the SARS-CoV-2 pandemic), storage of specimens may be deferred when samples are not collected on site.

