Primary efficacy outcome. All subjects will undergo a treatment interruption designed to evaluate the primary outcome of "post-treatment control" (PTC). The proportion of individuals who achieve PTC will be tabulated and a 2-sided 95% confidence interval obtained by exact calculations for the binomial distribution. For those who initiated ART during acute infection, a literature review indicates that no more than 15% PTC would be expected without intervention. For those who initiated during chronic infection, no more than 5% PTC would be expected. These maximum expected rates will serve as the null hypothesis for our P-value calculations. Evaluation of the acute group will be the primary analysis, while evaluation of the chronic group will be exploratory and provide initial preliminary information on generalizability.

Using standard and innovative measures of immunogenicity, we will determine the capacity of our vaccine strategies to stimulate broad, functional T cell responses against novel HIV epitopes, and comprehensively

characterize the impact of the vaccine on several innate and adaptive immune parameters. The size of the active and latent reservoirs before, during and after vaccination will be measured.

Power calculations. For the acute group, observing 6 or more PTC among N=15 (40%) will result in $P < 0.05$ versus the null hypothesis of 15%, and the study will have $\geq 80\%$ power if the true chance of PTC with intervention is $\geq 47\%$.

For the chronic group, observing even one PTC (20%) would provide some indication of promise, and observing 2 PTC (40%) would produce $P < 0.05$ versus the null hypothesis of 5%.

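### The two operational rules for post-treatment control use viral load only, and the plan has no biological check that a participant counted as a controller is off ART

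*Combined protocol and SAP*

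**What the plan says.** Section 15.4 takes its PTC definition from a published cohort, in which controllers had stayed off ART for at least 24 weeks. It then sets two routes to success. The first covers "subjects who fail to show any consistent rebound above 400 copies RNA/mL between Week 12 of the ATI" and Week 36. The second covers participants who rebound and later reach 24 weeks of control. Failure means a need to resume ART because of viremia, falling CD4+ counts or clinical events. The synopsis uses a different viral load threshold (below 50 copies/mL), but its endpoint definition also rests on viral load.

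On supply, Section 7 says: "Subjects must provide their own antiretroviral drugs". On recording, Section 9.1 says that at each visit "all additions or discontinuations of prescription medications should be recorded", and Section 16.2 adds an interviewer-administered questionnaire that covers ART use and adherence. Section 9.10 measures levels of the two antibodies every two weeks for 24 weeks of the interruption. Neither the rest of Section 9 nor the schedule in 10.12 lists an antiretroviral level.

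Under the schedule, plasma is stored every two weeks from study Week 34 to Week 58, then at Weeks 62, 70, 78 and 86. For remote draws, the note in 10.12 says "storage of specimens may be deferred when samples are not collected on site".

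On the decision rule, Section 15.6 says "For the acute group, observing 6 or more PTC among N=15 (40%) will result in" P below 0.05 against a null of 15%.

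**The concern.** What the trial observes is viral load after ART is stopped, so being off ART is part of what the endpoint means. A participant who went on taking ART, or restarted it and continued without saying so, would show no sustained rebound, or would re-suppress after one. Either pattern meets a success route and no failure criterion. The resulting error runs one way, towards efficacy. There is no concurrent control group in which the same error could appear, and the primary claim may rest on about six people. The plan tracks one source of residual antiviral effect, the antibodies, but not the other.

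**Working it through.** **Inputs.**
- Primary group N = 15, success boundary 6 (Section 15.6).
- Null rate p0 = 0.15 (Section 15.6: "a literature review indicates that no more than 15% PTC would be expected without intervention").
- At least 80% "power if the true chance of PTC with intervention is" 47% or more (Section 15.6).
- Test against the null rate "with a P-value obtained by likelihood ratio test" (synopsis, efficacy evaluations); sidedness is not stated.
- Number of undisclosed users k: an assumption, shown from 0 to 3, because the documents give no rate. Each is taken to be suppressed throughout and counted as PTC.

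**1. The plan's own figures.** Exact upper tail: P(X ≥ x), X ~ Bin(15, 0.15). Likelihood ratio statistic: 2[x ln(p̂/p0) + (15−x) ln((1−p̂)/(1−p0))], p̂ = x/15, referred to chi-square with 1 df.

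| PTC | Exact P | LRT statistic | LRT P (two-sided) | Exact 95% CI |
|---|---|---|---|---|
| 5/15 | 0.0617 | 3.126 | 0.077 | 11.8% to 61.6% |
| 6/15 | 0.0168 | 5.500 | 0.019 | 16.3% to 67.7% |

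The stated boundary of 6 reproduces. Power of the rule is 78.8% at a true rate of 47% and 81.0% at 48%, so the power statement holds to within about one point. (A one-sided LRT would give P = 0.0385 at 5/15 and move the boundary to 5. The plan's boundary of 6 is used here.)

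**2. When one false success changes the result.** It does so only if exactly 5 of the other 14 are PTC: C(14,5) p^5 (1−p)^9.
- p = 0.15: 3.5%
- p = 0.30: 19.6%
- p = 0.40: 20.7%

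**3. Type I error of the rule with k undisclosed users.** The k users are certain successes, so the error is P(Y ≥ 6−k), Y ~ Bin(15−k, 0.15).

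| k | Type I error |
|---|---|
| 0 | 1.7% |
| 1 | 4.7% |
| 2 | 11.8% |
| 3 | 26.4% |

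Check for k = 1: the user would have been a failure with probability 0.85, so 0.0168 + 0.85 × 0.0352 = 0.0467.

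At a true rate of 30%, one false success raises the chance of a positive result from 27.8% to 41.6%.

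**4. The same by rate.** If each participant is an undisclosed user with probability q (assumption), the apparent rate under the null is 0.15 + 0.85q. The error is then 2.8% at q = 2%, 5.2% at q = 5% and 11.7% at q = 10%. It passes 5% at q of about 4.8%. The null is described as a maximum. If the natural rate were 10% (assumption), the figures at the same q would be 0.5%, 1.4% and 4.9%.

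**5. Samples available.** ATI Weeks 12 to 36 are study Weeks 46 to 70 (34 + 12 and 34 + 36). If all draws are on site, plasma is stored in that window at Weeks 46, 48, 50, 52, 54, 56, 58, 62 and 70, which is nine samples.

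**The case against.** Several points on the other side stand.

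- A reader might infer that the endpoint ignores ART status altogether. It does not: the cohort definition quoted in 15.4 requires being off ART. What is missing is that condition in the two operational rules, a means of verifying it, and a rule for a positive finding.
- Concealment is not shown to be likely. Section 10.9 restarts ART at the participant's request, Appendix C makes the interruption a separate opt-in, Appendix B repeats counselling every 4 to 6 weeks, and Section 15.1 expects little non-adherence. Worry about transmission may lead to an open restart.
- That participants hold a supply during the interruption is an inference from Section 7. Nothing contradicts it, but nothing states it. The consent form and counselling checklists are not part of the text reviewed.
- Occasional doses need not produce a success. Viral load is measured weekly for 24 weeks and then every two weeks, so the problem is mainly sustained use.
- The 15% null comes from a literature review. If those studies did not verify ART absence either, the comparator carries some of the same error, which would partly offset it. The documents do not settle this.
- Section 15 says interpretation will not rest on the 0.05 threshold alone.

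None of this supplies a check. Open restart and counselling reduce the chance of hidden use but would not reveal it.

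**Conclusion.** The gap is real and limited. As written, sustained undisclosed ART use would be scored as PTC, and nothing in the readable text would detect it. No figure in the plan is wrong.

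A tempting stronger reading is that a single hidden user is enough to overturn the primary result. That is true only at the boundary, when exactly 5 of the other 14 are controllers (3.5% at a true rate of 15%, about 20% at 30% to 40%). One such user leaves the type I error just under 5%, at 4.7%; two or three take it to 11.8% and 26.4%. These sizes assume all 15 planned participants are analysed, users suppressed throughout, and a natural rate at the 15% maximum. With a lower natural rate the inflation is smaller. The number of users is an assumption throughout.

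The case for acting does not depend on hidden use being common. Each apparent controller carries much of the conclusion, and most of the material for verification is already being stored.

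**What to change.** In Section 15.4:

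1. State that both success routes require absence of ART.
2. Before PTC classification is final, test plasma already stored during the interruption from each provisional controller for the components of that person's pre-interruption regimen, at several points in the control window and at any re-suppression after a rebound.
3. Count a participant with drug detected in that window as not PTC in the primary analysis, and report the result with and without this reclassification.
4. Where remote draws left no stored plasma, report ART absence as unverified. Keeping an aliquot from remote draws is optional, since it adds processing and shipping where storage was deliberately waived.

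The cost is modest: six provisional controllers with three or four samples each would be 18 to 24 samples. Testing stored samples needs no new visit or procedure. The downsides are the possible loss of an apparent success and limited sensitivity to intermittent use after Week 58. From then on stored samples are 4 to 8 weeks apart, and Section 1.11 expects regimens to include rapidly cleared drugs. A clean result therefore supports ART absence but does not prove it.
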